Hypothesis #1B: *Whole blood resuscitation will be associated with a lower incidence of 12 hour and 24 hour mortality, a lower incidence of death from exsanguination, incidence of MOF, nosocomial infection, improved transfusion ratios, lower overall blood transfusion requirements and shorter time to hemostasis as compared to those resuscitated with component therapy.*

Hypothesis #1C: *Whole blood resuscitation will be associated with an improved Glasgow Outcome Score-Extended at 6 months post injury as compared to those resuscitated with component therapy in patients with traumatic brain injury.*

Hypothesis #2A: *A nadir prehospital and acute phase resuscitation systolic blood pressure greater than or equal to 120 mmHg will be associated with improved traumatic brain injury outcomes at discharge and at 6 months.*

Linking Investigations in Trauma and Emergency Services

Task Order 2: Shock, Whole blood and Assessment of TBI (SWAT)

Hypothesis #2B: *The magnitude of the dose depth curve of systolic blood pressure during the prehospital and acute phase resuscitation will be associated with neurological outcome differences at discharge and at 6 months following traumatic brain injury.*

Research Design and Methods

Study Design: The LITES Network will perform a multicenter, prospective, observational cohort study over a 4 year period to determine the impact of whole blood resuscitation in trauma patients with hemorrhagic shock at risk of large volume resuscitation with and without TBI. Early whole blood resuscitation will be compared to standard component resuscitation. The study will also further characterize blood pressure and resuscitation endpoints in poly-trauma patients with traumatic brain injury. Six trauma sites with appropriate characteristics will be selected from network sites across the country. (Figure 2)

Figure 2

Study Setting: The study will be performed utilizing busy level I trauma centers from within the LITES Network located across the country, at sites where either whole blood has currently been incorporated into standard of care or where component blood transfusion is being utilized for patients in hemorrhagic shock at risk for large volume resuscitation. Due to the paucity of trauma centers who are currently utilizing whole blood for trauma patients as standard of care, the potential to incorporate additional sites may be required over time.

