Primary Study Outcome: The cohort study will be principally powered using 4 hour mortality as the primary outcome. This outcome was found to be significantly different across treatment arms in the recent PROPPR trial and early mortality time points have recently been recommended and deemed most appropriate for hemorrhagic shock clinical trials.^{24,43} Promoting survival beyond this time period may represent the critical period that is required for an injured patient to be transported to a higher echelon of care, particularly when injury occurs in austere environments.

Secondary Non-TBI Clinical Outcomes: Secondary clinical outcomes will include 12 hr mortality, 24hr mortality, 28 day mortality, time to hemostasis (defined by a WB or PRBC transfusion rate; ≤ 1 unit/hour and surgeon directed intraoperative assessment), death from exsanguination/hemorrhage, blood and blood component transfusion requirements (over 1st four hours and total at 24hrs), Multiple Organ Failure, nosocomial infection, transfusion reaction, venous thromboembolism (VTE), ICU free days and ventilator free days.

TBI Specific Outcomes: For the overall TBI subgroup, the principle outcome will be 6 month Extended Glasgow Outcome Scale (GOS-E). Additional TBI specific outcomes will include hemodynamic parameters (serial systolic and diastolic blood pressure and heart rate measurements), prehospital, arrival, serial and discharge Glasgow Coma Scale scores, need for craniectomy/craniotomy, need for mannitol administration, need for paralysis, need for barbiturate coma, need for hypertonic saline administration, need for ICP monitoring, ICP pressures (initial, max daily x 7 days), TBI progression based upon serial CT imaging in initial 48 hours and Galveston Orientation and Amnesia Test (GOAT score) at discharge. Each accrual site will transfer the TBI patient's name, contact information, and basic injury characteristics, GOAT results, and discharge disposition to the Clinical Coordinating Center in Pittsburgh.

Linking Investigations in Trauma and Emergency Services

Task Order 2: Shock, Whole blood and Assessment of TBI (SWAT)

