Death from Exsanguination/Hemorrhage: Those patients who succumb on the operating table, IR suite or ICU due to uncontrolled coagulopathy or hemorrhage in the first 4 hours from arrival will have their mortality classified as exsanguination/hemorrhage. This will be determined by the individual trauma surgeon at the time of the event.

Acute Hemolytic Transfusion Reaction: We will utilize and characterize acute hemolytic transfusion reactions as defined by the CDC/National Healthcare Safety Network (NHSN) Hemovigilance Surveillance definition (www.cdc.gov/nhsn).

Linking Investigations in Trauma and Emergency Services

Task Order 2: Shock, Whole blood and Assessment of TBI (SWAT)

Galveston Orientation and Amnesia Test (GOAT): For TBI subjects, we will obtain the GOAT score at the time of discharge and the calculated score per standard methods.⁴⁸ (Figure 4) GOAT is a 10-item questionnaire used to quickly assess post-traumatic amnesia following head injury. The GOAT is read orally to the patient and may be easily administered at the bedside. The total score accounts for orientation of person, place, and time, and recollection of events pre and post-injury. Cutoff scores are available to identify abnormal, borderline, and normal orientation and it will additionally determine if a subject is able to provide continuing participation consent if consented by proxy.

Extended Glasgow Outcome Scale (6 months-GOSE): For TBI subjects, the GOSE score will be obtained at 6 months +/- 1month by hone survey or direct patient contact, whichever is feasible. For those TBI subjects who were unable to consent at discharge, the GOAT will be administered to assess their ability to provide direct consent, prior to the administration of the GOSE. When the assessment is done by phone, the verbal consent of participants who have regained the ability to consent, will be obtained to allow the GOSE to be completed. The score is able to characterize 6 month functional status into 8 well defined categories as shown in (Figure 5).

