Sample Tracking, Management and Storage: After sample obtainment, processing and storage, samples will initially be batched sent to the University of Pittsburgh biological sample repository where it will be tracked, managed and stored until the necessary translational or mechanistic measurement are performed. The CCC and DCC have a long track record of coordinating such processes.

Power Analysis: The prospective cohort study will utilize time to 4 hour mortality for its primary outcome to power the study. Based upon the 6 LITES Network sites admission history that will be utilized and their respective volume of hemorrhagic shock patients meeting inclusion and exclusion criteria and a 3.5 year enrollment time period, we plan to initiate sampling on 1,050 patients over the enrollment time period of the study. With an 85% consent rate which is an estimate based upon prior studies of similar nature, we will consent for participation 892 patients for the study. With an estimate baseline rate of 4 hour mortality of 11.1 % derived from the PROPPR study, there will be 90% power to detect a hazard ratio of 1.9.

Calculations are based on the primary aim of the study based on the following assumptions:

- Type I error rate of 0.05
- Two-sided alternative hypothesis

Linking Investigations in Trauma and Emergency Services

Task Order 2: Shock, Whole blood and Assessment of TBI (SWAT)

- 6 sites will be involved, three whole blood and three component sites
- Each site will enroll 175 participants in 3.5 years of enrollment, of which, 85% will be eligible for the study (149)
- The calculations are based on Cox proportional hazard model
- A 4 hour event rate in the control (non-whole blood) group of 0.111

The power calculations for these secondary aims are presented below. When reporting the results of the analyses, caution will need to be taken with respect to the interpretation of the findings since they are secondary in nature.

The secondary outcomes in Aim 1B include binary outcome, continuous outcomes, and time to event outcomes. For the binary outcomes, the odds ratio that can be detected is presented in Table 1. For the continuous outcome, the effect size that can be detected is 0.13. Finally, for the time to event outcomes, the hazard ratio that can be detected over a range of event rates in the control group is also presented in Table 1.

Event Rate	.1	.2	.3	.4	.5	.6
Odds Ratio	1.76	1.56	1.49	1.46	1.46	1.48
Hazard Rate	2.69	1.70	.37	.30	.27	.30

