- For Aim 1C, a nonparametric analysis of variance will be used to compare the distribution of the GOS-E between the two groups. An effect size of 0.17 could be detected.
- For aim 2A, a nonparametric analysis of variance will be used to compare the distribution of the GOS-E between the two groups. An effect size of 0.28 could be detected.
- For aim 2B, a nonparametric correlation coefficient will be used to assess the association between GOS-E and the area under the systolic blood pressure curve. For each, a 95% confidence interval with a width of 0.19 can be estimated.
- For all secondary analyses, the type I error rate was set to 0.05, with a two-sided alternative hypothesis, and 90% power. For the Aim 1, the sample size will be 1,190. For Aim 2, the sample size will be limited to those with a traumatic brain injury. For the purposes of this study, this is expected to be 35% or a total of 417 participants.

Analyses

AIM#1: The analysis will begin by describing the baseline demographic and clinical characteristics of the overall population and then stratified by whole blood usage. The characteristics will be

Linking Investigations in Trauma and Emergency Services

Task Order 2: Shock, Whole blood and Assessment of TBI (SWAT)

compared among those who receive and who do not receive whole blood. For discrete variables, proportions will be generated and a chi-square test will be used to test for differences between the proportions. For continuous characteristics, means (medians) and standard deviations (interquartile ranges) will be calculated and t-tests (Wilcoxon) will be used to compare the means (distributions) among those who receive and do not receive whole blood.

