Interim Analysis: There will be two aspects of the interim analysis. First, for efficacy, the Lan and Demets approach will be utilized to conduct the interim efficacy analysis. This approach is preferable over other approaches because it is flexible to the number of interim analyses conducted during the course of the study. The Lan and DeMets approach requires the use of a spending function to allocate the type I error to the interim analysis. The O'Brien and Fleming spending function which minimizes the type I error allocated to the interim analysis, saving the vast majority for the primary analyses will be used. For the proposed interim analysis, assuming that 50% of the study will be completed, it is estimated that the type I error allocated to the interim analysis will be 0.005, leaving 0.048 of the type I error for the primary outcome analysis.

Linking Investigations in Trauma and Emergency Services

Task Order 2: Shock, Whole blood and Assessment of TBI (SWAT)

Time Line: The study will occur over a 4 year period with a 6 month start up period, an interim analysis at 2 years and a 3.5 year enrollment period.

Linking Investigations in Trauma and Emergency Services

Task Order 2: Shock, Whole blood and Assessment of TBI (SWAT)

BIBLIOGRAPHY

3. Hoyt DB. A clinical review of bleeding dilemmas in trauma. *Semin Hematol*. 2004;41(1 Suppl 1):40-43.

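### Start-up plus enrollment fills the stated 4 years, leaving no time for the 6-month GOS-E in the last 12 to 14% of TBI enrollees

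*Combined protocol and SAP*

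**What the plan says.** The Time Line section gives the whole calendar in one sentence: "The study will occur over a 4 year period with a 6 month start up period, an interim analysis at 2 years", ending with "an interim analysis at 2 years and a 3.5 year enrollment period". The Study Design section repeats the total ("prospective, observational cohort study over a 4 year period to determine the impact of whole blood resuscitation"), and the Power Analysis repeats the enrollment length ("a 3.5 year enrollment time period, we plan to initiate sampling on 1,050 patients over the enrollment time period of the study"). No section lists follow-up or close-out time after the last enrollment.

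Under TBI Specific Outcomes: "For the overall TBI subgroup, the principle outcome will be 6 month Extended Glasgow Outcome Scale (GOS-E"). The Extended Glasgow Outcome Scale definition sets the timing: "the GOSE score will be obtained at 6 months +/- 1month", by phone or direct contact. Table 1 has the same column. Hypotheses 1C, 2A and 2B all use this score.

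For the size of the TBI subset, the Power Analysis says "this is expected to be 35% or a total of 417 participants", with no deduction for incomplete follow-up.

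**The concern.** If start-up and enrollment together use the full 48 months, a TBI patient enrolled at the end has a 6-month assessment due at month 54, after the study is stated to have finished. The duration and the principal TBI endpoint then cannot both hold for the last enrollees.

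Two things are at stake. One is precision: the figures for the GOS-E analyses assume that every TBI participant contributes a score. The other is selection by outcome. On the 8-category scale, death is category 1 and is known as soon as it happens, whereas a survivor's score exists only after about 6 months. Among patients enrolled too late to be assessed, those who died would have a score and those who lived would not.

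**Working it through.** **Inputs.** Total 48 months, start-up 6 months, enrollment 42 months (Time Line). GOS-E at 6 months, window 5 to 7 (Extended Glasgow Outcome Scale definition). TBI share 35%, stated as 417 (Power Analysis). Consented sample 892 (Power Analysis).

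**1. The plan's own total.** 6 + 42 = 48 months = 4.0 years. The stated duration reproduces exactly, with nothing left over.

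**2. The last assessments.** A patient enrolled at month 48 is due at month 54, with a window from 48 + 5 = 53 to 48 + 7 = 55.

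**3. Share affected.** The documents give no accrual curve, so I assume uniform accrual over 42 months.
- Enrolled after month 43, so even the earliest in-window assessment falls after month 48: 5/42 = 11.9%.
- Enrolled after month 42, so the 6-month point itself falls after month 48: 6/42 = 14.3%.
- Enrolled after month 41, so the window is cut short: 7/42 = 16.7%. Part of this last group can still be assessed in the window by month 48, so 16.7% is not a missing share.

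**4. Counts.** The Power Analysis carries two totals: 892 consented, and 1,190 for the secondary aims. Both bases are shown.
- 0.35 × 892 = 312. Then 312 × 5/42 = 37 and 312 × 6/42 = 45.
- 0.35 × 1,190 = 416.5, the stated 417. Then 417 × 5/42 = 50 and 417 × 6/42 = 60.

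These are upper limits on missing scores. If a fraction f of late enrollees has died by month 48, the missing count is multiplied by (1 − f). The documents do not give f at 6 months.

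**5. Direction.** For patients enrolled after month 43, no survivor can have an in-window score by month 48, so every score available for them is a 1.

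**6. Hypothesis 2B precision.** The stated 95% interval width is 0.19. On the Fisher scale, width = 2 × 1.96/√(n − 3).
- n = 417: 3.92/√414 = 0.193, which reproduces the plan.
- n = 417 − 50 = 367: 3.92/√364 = 0.205.
- n = 417 − 60 = 357: 3.92/√354 = 0.208.

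The width goes from 0.19 to about 0.21.

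**7. Detectable standardized difference.** As an index only, for two equal groups, 90% power and two-sided 0.05: d = (1.960 + 1.282)/√(n × 0.25) = 6.484/√n.
- From 312: 0.367, rising to 0.397 at n = 267.
- From 417: 0.318, rising to 0.343 at n = 357.

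The ratio is √(42/36) = 1.08 on either base, an 8% increase. With 12% lost it is √(42/37) = 1.07.

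**The case against.** The strongest reply is that the Time Line is a single sentence on start-up, interim analysis and enrollment, and does not say that follow-up stops at month 48. The GOS-E can be done by phone, and sites pass TBI patients' contact details to the Clinical Coordinating Center, so late calls need not depend on sites still enrolling. This stands in part: the documents do not show that late scores would be impossible to obtain. They do state that the study takes place over 4 years, put the interim analysis at 2 years on the assumption that half the study is complete, and name no later period. The stated duration and endpoint conflict as written.

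Start-up might also run inside enrollment. Enrollment would then end at month 42, with the last GOS-E due at month 48 and its window closing at month 49. Nothing in the documents supports that overlap.

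A reader might infer three stronger things that the documents do not support.
- **That the time line cuts 417 scores to 267.** The step from 417 to 312 comes from the separate conflict between 1,190 and 892. Only 312 to 267 belongs to the time line, before allowing for deaths.
- **That a detectable difference of 0.40 should be set against the stated effect sizes of 0.17 (1C) and 0.28 (2A).** The plan does not define its metric. The formula in step 7 gives 0.19 at n = 1,190 (the stated Aim 1 base) and 0.32 at n = 417, so neither figure reproduces even with no loss. The 50:50 split is also an assumption: the Whole Blood Transfusion Sites section aims for 33% of patients from whole-blood sites, and the split for 2A is not given.
- **That the missing scores would fall mainly on whole-blood patients.** The plan mentions only a potential to add whole-blood sites, gives no number, and its power assumptions use three sites of each kind.

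**Conclusion.** The point holds as a conflict between the stated duration and the stated principal TBI outcome. Read consecutively, start-up and enrollment use all 48 months. With uniform accrual, 12% of TBI enrollees cannot be assessed in the window by month 48 and 14% reach the 6-month point after it, before subtracting deaths already known.

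The loss of precision attributable to the time line is small. The more serious consequence is that missingness would depend on outcome if the analysis used whatever scores exist at month 48. The size of that tilt cannot be computed, because the documents give no 6-month mortality for TBI patients.

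The gap is confined to the 6-month parts of Hypotheses 1C, 2A and 2B. The 4-hour primary outcome and the 12-hour and 24-hour outcomes are untouched.

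**What to change.** Preferred: restate the study duration so that GOS-E follow-up runs to 7 months after the last enrollment, that is to about month 55 (55/12 = 4.6 years), and say that the 6-month analyses wait for it. The cost is some coordinator time for phone follow-up.

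If 4 years is fixed: restrict the GOS-E analyses to TBI patients enrolled by a date set in advance, about study month 41 so that the full window fits (41 + 7 = 48). Apply the cut-off to deaths and survivors alike. Then restate the sample and precision: 35/42 of the TBI patients is 260 of 312, or about 347 of 417, and at 347 the 2B width is 3.92/√344 = 0.21. Restating these figures costs nothing beyond the smaller sample. The 892 and 1,190 totals need to be reconciled first, so that the restated sample rests on one base.
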